8.2.3.2. Adverse Events

- **All adverse events**

The number and proportion of patients with adverse events will be tabulated by SOC and PT.

- **Adverse events by serious/non-serious**

The number and proportion of patients with serious adverse events will be tabulated by SOC and PT. The same tabulation will be performed for non-serious adverse events.

8.2.3.3. Other Endpoints

Not applicable.

8.2.3.4. Subgroup Analysis

To evaluate the relationship between patient background factors and the development of adverse drug reactions, risk ratio and risk difference between subgroups will be calculated for the incidence of adverse drug reactions in accordance with Section 8.1.3. For subgroups with risk ratio ≥ 2 or ≤ 0.5 , the number and proportion of patients who experienced adverse drug reaction will be summarized for each factor, using SOCs and PTs.

In addition, the number and proportion of patients who experienced adverse drug reaction will be tabulated by SOC and PT for each of the following factors.

- Age [elderly (≥ 65 years), non-elderly (< 65 years)]
- Hepatic dysfunction [absent, present]
- Renal dysfunction [absent, present]
- HIV infection [absent, present]

8.2.3.5. Exploratory Analysis

The following exploratory analysis will be performed for factors affecting safety:

- For adverse drug reactions with high incidence ($> 10\%$), factors for development of adverse drug reactions will be examined using methods such as logistic regression analysis.
- To examine the effects of concomitant medications on development of adverse drug reactions, the number and proportion of patients by name of concomitant drug^c (drug subclassification and nonproprietary name) will be calculated by presence or absence of adverse drug reactions.

Additional exploratory analysis may be performed, as necessary. Among those exploratory analyses, only those that resulted in important interpretations will be reported.

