2.1. Study Design

This investigation is a multicenter open study in patients who received AMEPAROMO for treatment of intestinal amebiasis. Patients who have never been treated with AMEPAROMO will be enrolled using a central registration system. The observation period shall start on the day the treatment with AMEPAROMO begins (Day 1) and end on Day 10. The main effectiveness analysis item will be the proportion of cyst negative based on the results of examination of cysts up to 3 months after the completion of observation period (or discontinuation of treatment), and clinical response assessed by the investigator will also be evaluated. A target sample size of 100 patients was selected. The rationale for the target sample size is shown below.

- *Rationale*

The number of patients who will receive AMEPAROMO may be extremely small, but 100 patients were chosen as a sample size that can be collected during a certain period of time from the viewpoint of the feasibility of the study.

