3. INTERIM AND FINAL ANALYSIS

In this study, interim analyses for periodic safety update report will be performed periodically. At the time of interim analyses, only the analyses of items necessary for periodic safety update report among the statistical analyses specified in this plan will be performed. In addition, the final analysis for the application for reexamination will be performed. At the time of the final analysis, all analyses specified in this plan will be performed.

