4. HYPOTHESES AND DECISION RULES

4.1. Statistical Hypotheses

Because this study is not a confirmatory investigation, the tests are considered as exploratory tests.

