8.1.3. Analysis of Binary Data

The number of patients and proportion will be calculated. If the confidence interval of proportion is calculated, two-sided 95% confidence interval (exact method) will be calculated.

If the proportion is compared between subgroups, risk ratio and its 95% confidence interval, and risk difference and its 95% confidence interval will be calculated. If the number of patients in subgroups compared is less than 10, the number and proportion of patients will be calculated but risk ratio and its 95% confidence interval, and risk difference and its 95% confidence interval will not be calculated.

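### Unplanned exploratory analyses are reported only if judged important, by an undefined criterion and with no count of how many were run

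*SAP*

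**What the plan says.** SAP 8.2.3.5 names two exploratory safety analyses. One looks for factors behind adverse drug reactions with an incidence above 10%: "factors for development of adverse drug reactions will be examined using methods such as logistic regression analysis". The other tabulates concomitant drugs by presence or absence of adverse drug reactions. The section then opens the door to more work: "Additional exploratory analysis may be performed, as necessary". The next sentence sets the reporting rule: "Among those exploratory analyses, only those that resulted in important interpretations will be reported".

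SAP 8.2.4.4 names one exploratory effectiveness factor, the response to prior treatment, and then repeats the same two sentences.

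Four other places bear on the point:

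- SAP 4.1 sets the status of all tests: "Because this study is not a confirmatory investigation, the tests are considered as exploratory tests". SAP 4.2 gives no decision rules.
- SAP 3 makes a commitment about planned work: "At the time of the final analysis, all analyses specified in this plan will be performed".
- SAP 2.2 and Protocol 6 give, as the third objective, the factors that may affect safety and effectiveness.
- SAP 9 lists the listings and appendix forms to be produced. None of them records which exploratory analyses were run.

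**The concern.** The two sentences are an affirmative instruction to decide what is reported from what the result showed. That differs from leaving a detail open. An exploratory association can be weighed sensibly only if the reader knows how many were looked for. Here the number is open-ended, the filter is undefined and is applied after the data are seen, and the analyses left out leave no trace.

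The problem can run in two directions. A chance association may be reported without its denominator, and an uninformative-looking null, such as no association with a suspected risk factor, may go unmentioned. Either would distort what the report says on the third objective, as far as that rests on unplanned analyses. The final analysis supports the reexamination application (SAP 3), and Protocol 10 allows publication, so the report will have outside readers who cannot reconstruct the count.

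The sample size adds to this. The SAP says "100 patients were chosen as a sample size that can be collected during a certain period of time from the viewpoint of the feasibility", so precision was not a design consideration, and factor-by-factor estimates from about 100 patients will be imprecise.

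**Working it through.** The documents give no figure on this point, so there is nothing to reproduce. The check is mainly one of text, followed by an illustration.

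**Step 1: which analyses the rule covers.** The reporting sentence directly follows the one permitting additional analyses, so its natural reach is those additional analyses. Set against the rest of the SAP:

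| Analysis | Where | Specified in advance? | Under the reporting filter? |
|---|---|---|---|
| Adverse reaction incidence; proportion of cyst negative | SAP 8.2.3.1, 8.2.4.1 | Yes | No |
| Subgroup risk ratios and differences | SAP 5.3, 8.2.3.4, 8.2.4.3 | Yes | No |
| Named exploratory analyses | SAP 8.2.3.5, 8.2.4.4 | Yes | No, on the natural reading |
| Additional exploratory analyses | SAP 8.2.3.5, 8.2.4.4 | No | Yes |

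**Step 2: whether anything else supplies the count.** SAP 3 covers the performance of specified analyses; additional ones are by definition not specified. SAP 4.1 and 4.2 lower the claim made for any result but disclose nothing about how many were obtained. SAP 9 has no such listing. Nothing in the protocol requires one.

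**Step 3: illustration.** Inputs:

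- Number of additional analyses, k: not in the documents. Assumed values are 5, 10 and 20.
- Threshold for an apparent association: not in the documents. Assumed to be two-sided 5%, matching the 95% level of the intervals in SAP 8.1.3.
- No true effects, and independent analyses: both assumed.

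Chance of at least one apparent association = 1 − 0.95^k. Expected number = 0.05 × k.

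| k | 1 − 0.95^k | Expected number |
|---|---|---|
| 5 | 1 − 0.7738 = 0.226 | 0.25 |
| 10 | 1 − 0.5987 = 0.401 | 0.5 |
| 20 | 1 − 0.3585 = 0.642 | 1.0 |

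**Step 4: dependence.** All the analyses would use the same patients and overlapping factors, so independence will not hold exactly. The expected number, 0.05 × k, does not depend on independence. The chance of at least one does: it lies between 5% (analyses that coincide completely) and 0.05 × k, capped at 100%. The upper bounds are 25% for k = 5, 50% for k = 10 and 100% for k = 20. The conclusion does not need any particular value. The same reported finding means something different at k = 1 and at k = 20, and the plan does not let the reader know which applies.

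**The case against.** The strongest reply is that this is a single-arm, non-confirmatory drug use investigation. It says openly that its tests are exploratory, and the sentences sit under a heading that says so. The third objective is served mainly by analyses fixed in advance, and the extra ones may never be run. Nobody expects a report to print every exploratory look. Most of this stands, and it is why the point is modest. What it leaves untouched is the missing count: the exploratory label tells a reader to be cautious but not how cautious.

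Three stronger readings are tempting and are not supported.

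- *A reader might take the 13 safety background factors in SAP 5.3 as the number of looks and compute 1 − 0.95^13 = 49%.* Those factors are prespecified, SAP 8.2.3.4 says their risk ratios and differences will be calculated, and the reporting filter does not apply to them. Their number is visible in the plan.
- *A reader might infer that only positive findings will be reported and that nulls will disappear.* The criterion is undefined and could include an informative null. The text supports a result-dependent filter, not a stated rule to publish positives only.
- *A reader might infer that all reported factors are biased away from the null.* That could apply only to the optional additional analyses.

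It is also fair to object that the plan states no test level, so equating importance with a 5% threshold is an assumption. That stands, and the percentages are offered only on that footing.

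**Conclusion.** The concern holds, limited to the unspecified additional exploratory analyses in SAP 8.2.3.5 and 8.2.4.4. For these, the plan sets an undefined, result-dependent criterion for reporting and requires no disclosure of how many were run, so a reported additional finding on factors affecting safety or effectiveness cannot be calibrated.

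Severity is modest, because neither the main results nor any prespecified analysis depends on the filter. The figures of 23%, 40% and 64% show how quickly the count comes to matter. They do not estimate what this study will produce, since they rest on an assumed number of analyses, an assumed 5% threshold, no true effects and independence. The textual finding rests on none of these. It rests on reading the reporting sentence as referring to the additional analyses it follows.

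**What to change.** In both SAP 8.2.3.5 and SAP 8.2.4.4, replace the reporting sentence with:

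> All additional exploratory analyses performed will be listed (question, population, outcome, method) in the report or an appendix with a brief statement of the result, and labelled post hoc; the text may discuss only the important ones.

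This keeps the freedom to run further analyses and to concentrate the discussion on those that matter, and it gives the reader the denominator. Full output for every analysis is not needed; one line each is enough. The cost is one sentence in each of two sections, a running log kept during the analysis, and a short appendix table. No endpoint, analysis set, sample size or data collection changes.

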8.2.4. Effectiveness Analysis

8.2.4.1. Proportion of Cyst Negative

In the cyst analysis set, the number and proportion of patients with negative results in the examination of cysts after AMEPAROMO treatment will be calculated. The 95% confidence interval of the proportion of cyst negative will be calculated. The proportion of cyst negative will be calculated using the following equation:

$$\text{Proportion of cyst negative (\%)} = \frac{\text{Number of patients with cyst negative}}{\text{Number of patients with cyst positive} + \text{number of patients with cyst negative}} \times 100$$

8.2.4.2. Clinical Response Rate (assessed by the investigator)

In the clinical response analysis set, the number and proportion of patients in whom the clinical response (assessed by the investigator) after AMEPAROMO treatment is effective will be

^c: The presence or absence of concomitant medications will be determined by excluding concomitant medications started to be used after the day of onset of the last adverse drug reaction observed during the observation period plus 28 days.

calculated as the clinical response rate. The 95% confidence interval of the AMEPAROMO rate will be calculated. The clinical response rate will be calculated using the following equation:

$$\text{Clinical Response rate (\%)} = \frac{\text{Number of patients with "effective"}}{\text{Number of patients in the clinical response analysis set excluding "indeterminate"}} \times 100$$

8.2.4.3. Subgroup Analysis

For each factor specified in Section 5.3, risk ratio and risk difference between subgroups will be calculated for the proportion of cyst negative and clinical response rate in accordance with Section 8.1.3.

8.2.4.4. Exploratory Analysis

The following exploratory analysis will be performed for factors affecting effectiveness:

- Clinical response of prior treatment [effective, not effective, indeterminate]

Additional exploratory analysis may be performed, as necessary. Among those exploratory analyses, only those that resulted in important interpretations will be reported.

9. LISTINGS

[figure not shown]
The following listings will be prepared. Listings with “Intext” specified following the listing title indicate listings that will be specified in the text of periodic safety update reports and documents for application for reexamination as they are.

- Listing of patients
- Listing of patients with adverse events
- Listing of patients with adverse drug reactions (Intext)
- Listing of patients with adverse drug reactions among patients excluded from the safety analysis set
- Listing of patients with serious adverse drug reactions (Intext)
- Listing of patients with serious adverse events
- Listing of patients with adverse drug reactions among patients with hepatic dysfunction (Intext)
- Listing of patients with adverse drug reactions among patients with renal dysfunction (Intext)
- Listing of elderly patients with adverse drug reactions (Intext)
- Listing of patients with adverse drug reactions among pregnant and parturient women (Intext)
- Listing of effectiveness in pregnant and parturient women (Intext)
- Listing of contraindicated patients

- Listing of concomitant medications by patient
- Listing of patients with overdose
- Patient listing of changes in intestinal bacterial flora (Intext)

Furthermore, the following tables corresponding to appendix forms to periodic safety reports (PSUR) and documents for application for reexamination will be prepared:

- PSUR: Appendix Form 2 (Status of development of adverse drug reactions and infections in post-marketing surveillance, etc.)
- Reexamination: Appendix Form 15 (List of adverse drug reactions and infections)
- Reexamination: Appendix Form 16 (Overview of patients in post-marketing surveillance, etc.)

090177e1918e8907\Approved\Approved On: 26-Jul-2019 07:07 (GMT)
